	2, Study Synopsis	
 -Based on pre-clinical data suggesting that the activation and expansion of CMV pp-65-specific T cells can be enhanced through modification of the RNA encoding pp65 with a full-length LAMP fusion protein, influenza virus matrix M1 was replaced with full-length LAMP protein. -Saline skin prep was removed and all subjects randomized to receive DCs will receive Td skin prep based on clinical data showing prolonged survival. -To serve as a true control, GM-CSF was removed from the PBMC arm. -Reference to Nature paper was added. -The primary objective was modified to evaluate the impact of Td on overall survival. -The secondary objectives were modified to evaluate progression-free survival and immunologic effects of short versus full-length LAMP. -Modifications were made to clarify inclusion criteria and timing of eligibility assessments. -Since manufacturing processes are different among the arms, the study design was changed to "single-blind". -Randomization was changed to "prior to leukapheresis" to allow for adequate manufacturing time for each arm. -MRI/MRS imaging of inguinal lymph nodes replaced SPECT/CT imaging as the method to assess the impact of DC vaccination and unpulsed PBMC vaccination at inguinal draining lymph nodes. -Immune monitoring time points were expanded to include collection around MRI/MRS. -nMR analysis of urine was added as a biological correlate. -Imaging time points were amended to align with clinical standards. Minor editorial changes for clarity.
	3, Study Schema	
 -Study schema was modified to reflect new study design.

Summary of Protocol Changes		
Version Date	Sections Revised	Purpose
	4, Abstract	
 -Reference to EGFRvIII data removed. -Data related LAMP fusion proteins added. Study aims modified to align with primary and secondary objectives.
	5, Hypothesis and Objectives	
 -Sections modified to align with modified treatment arms. -New section added to outline exploratory objectives.
	6, Background and Significance	
 -Minor editorial, formatting, and clarification changes. -Section modified to delineate between ATTAC- and ATTAC-GM trials. -Survival data added for ATTAC-GM trial.
	7, Study Rationale	
 -Reference to in vitro full-length LAMP data added.

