	Synopsis, 9.1 Overview, 15.1 Study Design Overview	-Sections revised to increase total enrollment number to reach the study target of 120 evaluable subjects. The study target of 120 evaluable patients (defined as having received at least one study vaccine) as described in section 15.2 Sample Size Justification for Vaccine Comparison remains unchanged. -Based on current withdrawals due to early progression, AEs that preclude vaccination, subjects requests or screen-failure rate, we plan to enroll up to 200 subject to achieve the study goal of 120 evaluable patients.
	10.6, Concomitant Medications	- Section revised to clarify the use the use of bevacizumab for patients experiencing symptomatic radiation necrosis.
20211021	9.6, Removal of PBMCs by Leukapheresis	- Section revised to add language related to placement of central venous catheter and potential use of fluoroscopy.
	13.5.7 Central Venous Catheter	- Section 13.5.7 Central Venous Catheter added to the potential risk section of the protocol to outline the potential risk associated with placement of a central venous catheter
20220119	Title Page	-Updated to reflect change in personnel. The UFH Cancer Center will provide ongoing statistical support.
20230509	Title Page	-Updated to reflect change in personnel.
	10.1 Enrollment	- Molecular diagnostics were added to the study requirements for data analysis. With recent advancements on tumor molecular aberrations significance for high-grade brain tumors diagnosis and the understanding of their impact on biological mechanism of treatment resistance and patients' prognosis, MGMT-promoter and IDH-1/2 status have become a requisite for data analysis on glioblastoma studies.
	12. Immunological Response Evaluations	- Section has been updated to include correlative studies that will be conducted for data analysis and reporting at the end of the study.
20231122	Title Page	- IND Sponsor updated to reflect change from Immunomic Therapeutics back to UF. -Update study personnel to reflect current personnel.
20241007	15.3.2 Secondary Biological Objectives	- Section updated to ensure consistency with the analysis outlined in section 12.3 Multiplex Cytokine Quantification. Cytokines array analysis results will be reported as part of the study's secondary biological objectives.

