Patients who have been enrolled in the study but are no longer eligible to receive study treatment for reasons other than progression are allowed to receive vaccines that have been generated for them at the discretion of the PI. They will be replaced for purposes of study endpoint if they do not meet criteria of an evaluable subject (received standard XRT/TMZ and received at least one DC vaccine). Such subjects would include: subjects who do not complete standard radiation treatment with concomitant TMZ, have prolonged interruption of treatment beyond allowable study guidelines. These patients will be included in the intent to treat analysis but excluded from the evaluable subjects analysis if disqualified prior to receiving first vaccine. Such subjects may receive QA/QC qualified DC vaccines according to study schedule with or without TMZ at discretion of the PI and in consultation with the treating neuro-oncologist (i.e. subjects removed for intolerance of TMZ treatment may discontinue or reduce TMZ dose as clinical management would dictate).

Given absence of curative treatment for GBM, release of vaccines to patients who have consented to the study but are unable to meet study requirements (most often chemotherapy intolerance) is deemed in best interest of the enrolled subjects and best utilization of cGMP manufactured autologous products. While these patients may be excluded from primary endpoint analysis of evaluable subjects, all toxicity monitoring and DLT stopping rules will apply to any subjects receiving DC vaccination.

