15 STATISTICAL METHODS AND DATA ANALYSIS

15.1 Study Design Overview

The primary goal of this randomized phase II study is to determine whether the addition of pp65-LAMP mRNA DC vaccination in adult patients with newly-diagnosed GBM receiving dose-intensified TMZ will be a treatment worthy of investigation in a large phase III study. A secondary

objective will be examination of the immunologic responses induced by full-length vs short LAMP sequences.

Although this randomized phase II study is comparative, it will not be definitive as the assessment will be conducted with a large false-positive rate. We have included a concurrently followed control arm in the trial design in lieu of a historical control group to ensure that appropriate comparisons can be made without concern that the patients receiving standard treatment differ in prognostic factors or standards of care (Rubinstein, 2009; Ratain and Sargent, 2009; Rubinstein et al., 2005).

We will randomize eligible patients, after enrollment, to one of 3 study arms in which they will receive 21-day TMZ concurrently with one of the following treatments:

Arm #	Vaccine	Skin Preparation
1	pp65-shLAMP mRNA DCs with GM-CSF	Tetanus
2	pp65-fLAMP mRNA DCs with GM-CSF	Tetanus
3	PBMCs	Saline

Randomization will be stratified by:

- Age 69 years old and younger; or 70 years old and older
- RPA Class (III, IV, or V)
- CMV seronegative or seropositive

We will use a permuted block randomization scheme with a 1:1:1 study arm allocation ratio and a block size of 6 within each stratum.

Adapted RPA Stages For Malignant Gliomas (Survival With Concurrent Temozolomide and Radiation Therapy vs Radiation Therapy alone)				
Stage	Characteristics	Median OS	2-year OS	p-value vs. control
III	Age <50, PS 0	21 vs. 15 mo	43% vs. 20%	p<0.0001
IV	Age <50, PS 1-2 Age >=50, Surgery, MMSE >=27	16 vs. 13 mo	28% vs. 11%	p<0.01
V	Age >=50 and either Biopsy only or MMSE <27	10 vs. 9 mo	17% vs. 6%	p=0.05

Approximately 200 patients will be enrolled in the study, randomized and receive “standard-of-care” radiotherapy concurrent with TMZ under the assumption that approximately 120 patients will be vaccinated according to treatment arm.

A Data Sharing Agreement has been established with Immunomic Therapeutics, Inc. and the University of Florida. A Limited Data Set will be sent to evaluate immunogenicity and clinical efficacy of the vaccine products used within this clinical trial (for patients treated at the UF site

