15.2 Sample Size Justification for Vaccine Comparison

The primary focus of this trial will be to assess the worthiness of pp65-LAMP mRNA DC vaccine for further investigation by comparing overall survival (OS) between the active treatment group (Arms 1 and 2 combined) and the control group (Arm 3). Because this test for efficacy will be made within the framework of a phase II trial, we have constrained sample size requirements to yield adequate power to detect a clinically relevant improvement in OS at the expense of the false positive rate (α -level or Type I error rate). Adopting guidelines proposed by Ratain and Sargent (2009) and Rubinstein et al (2005), our proposed sample size of $40 + 40 = 80$ patients in the treatment group and 40 patients in the control group will allow detection of a clinically relevant improvement in the median OS time of the treatment group with 90% power at a one-sided α -level of 0.2.

In determining the effect size that can be detected by our proposed sample size, we considered using as a control reference level the median OS estimate of 14.6 months (95% CI: 13.2 to 16.8) reported by Stupp et al (2005) for patients receiving radiotherapy plus TMZ (RT+TMZ) for newly-diagnosed GBM (40% of patients in the Stupp trial were grossly resected). In the Stupp trial, randomization occurred prior to any post-surgical treatment, and the timing of randomization in our study will be similar. However, in our study, patients will not begin to experience potential differential effects due to treatment until after their first vaccination, which will occur approximately 15 weeks after randomization. To determine an appropriate control reference level for median OS for an index day 15 weeks after randomization, we carefully transferred the coordinates of multiple points along the Stupp RT+TMZ OS curve into a statistical software package. We determined that median OS relative to a starting time 15 weeks after the Stupp index day would be 13.8 months. We also observed that RT+TMZ OS times appeared to approximately follow a Weibull distribution with a shape parameter = 1.20, indicating a slightly accelerating baseline hazard function. Upon examining in a similar manner the RT+TMZ OS curve reported in the paper by Gilbert et al (2013), we also observed approximately Weibull-distributed OS times with shape parameter = 1.16.

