15.3 Analytic Methods

15.3.1 Primary Objective and Secondary Clinical Objectives

We will use Kaplan-Meier survival curves and the log rank test to characterize and compare PFS and OS in patients who received pp65-LAMP mRNA DC vaccine (Arms 1 and 2) and in control patients (Arm 3). PFS is defined as the time between first vaccination and first documentation of either disease progression/recurrence, or death without prior progression/recurrence. Patients remaining alive without disease progression will have PFS censored at last follow-up. OS will be defined as the time between first vaccination and death, and will be censored at the last follow-up if death has not occurred. We will also perform a stratified analysis incorporating the three stratification variables (age, RPA class, and CMV sero-status) using Cox proportional hazards regression. The index day for all of our primary comparisons will be the time of the first vaccination. Because patients who fail to proceed to the first vaccination because of GBM recurrence or for other reasons cannot experience differential effects due to treatment arm membership, we will not perform an intent-to-treat analysis that includes these patients. We will perform an intent-to-treat analysis of OS and PFS that includes patients who begin the vaccination sequence but who do not receive at least three vaccinations because of recurrence or other reasons. OS and PFS times for adequately vaccinated patients who are lost to follow-up will be considered right-censored at the time of loss and will be included in all of our survival comparisons.

All subjects who receive at least one dose of DC vaccine will be considered evaluable for purposes of safety and toxicity.

All subjects who complete chemoRT and receive dose-intense adjuvant TMZ and at least 3 DC vaccines will be considered evaluable for purposes of the primary and secondary endpoints.

The impact of pp65-LAMP mRNA DC vaccine on PFS and OS in patients with gross total resection will also be explored using the log rank test and Kaplan-Meier curves, although our trial design may not necessarily achieve sufficient power to detect a clinically meaningful effect within this patient subgroup.

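### Section 15.3.1 rules out any survival analysis of all randomized patients, although up to about 40% may never reach vaccine 1 and section 9.8 says some of them will be in the intent-to-treat analysis

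*Combined protocol and SAP*

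**What the plan says.** Randomization comes before the first leukapheresis (sections 9.1 and 10.2) and so before chemoradiation. Section 15.2 places the first vaccination later, "which will occur approximately 15 weeks after randomization". Section 15.1 says "Approximately 200 patients will be enrolled in the study, randomized and receive" standard chemoradiation, with about 120 expected to be vaccinated.

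Section 15.3.1 starts both OS and PFS at first vaccination. Of patients who do not reach it, through recurrence or for any other reason, it says they "cannot experience differential effects due to treatment arm membership, we will not perform an intent-to-treat analysis that includes these patients". What it does call intent-to-treat is limited to patients who have begun the vaccine sequence. No other section plans a survival comparison of everyone randomized or a table of pre-vaccine loss by arm.

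Section 9.8 deals with patients who lose eligibility for study treatment. Those who lose it "for reasons other than progression are allowed to receive vaccines that have been generated for them at the discretion of the PI". It then adds: "These patients will be included in the intent to treat analysis but excluded from the evaluable subjects analysis if disqualified prior to receiving first vaccine".

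Section 15.1 explains why there is a concurrent randomized control: so that comparisons can be made "without concern that the patients receiving standard treatment differ in prognostic factors or standards of care".

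**The concern.** The argument in 15.3.1 is that treatment is the same in all arms until vaccine 1, so patients lost earlier carry no information about the vaccine. That is true of each such patient, but it does not protect the comparison of those who remain. The vaccinated groups stay comparable only if reaching vaccine 1 is independent of arm, or independent of prognosis.

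Dependence on prognosis is documented. The 20210810 entry in the Summary of Protocol Changes attributes the larger enrolment to "current withdrawals due to early progression, AEs that preclude vaccination, subjects requests or screen-failure rate".

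Independence from arm is not assured:

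- The trial is single-blind. The amendment log gives the reason: "Since manufacturing processes are different among the arms, the study design was changed to" single-blind. Personnel at the treating site perform the randomization (9.3), and the documents do not say that those who judge eligibility are blinded.
- Both products undergo release testing (9.6.1, 9.6.2), but the DC product also needs culture, electroporation and maturation.
- Eligibility, including absence of progression, is re-checked after randomization (8.2, 10.4). Whether a patient disqualified for another reason is still vaccinated is left to the PI (9.8).

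At stake is the comparability that section 15.1 gives as the reason for the control arm. As the plan stands, a reader could not check whether it survived to vaccine 1.

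**Working it through.** **The plan's own figure.** Inputs from section 15.2: hazard ratio (HR) 0.60, one-sided alpha 0.20, power 90%, 80:40 allocation, control median 13.8 months from vaccine 1. Schoenfeld's formula gives (0.8416 + 1.2816)² / [(2/9) × (ln 0.6)²] = 4.508 / 0.0580 = 77.7, or 78 deaths, against 77 stated. Power at 77 deaths is 0.898. The stated median gains and the times to 77 deaths also reproduce (for shape 1.20: +7.3 and 45.7 months). The design arithmetic is sound for the vaccinated set.

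**Size of the exclusion.** (200 − 120)/200 = 40%. With the superseded planning figure of 175, (175 − 120)/175 = 31%. The log shows that both totals allow for screen failures, so both are upper values. True loss among the randomized cannot be recovered from the documents.

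**Go boundary.** At 77 deaths the test is positive when the observed HR is below about exp(−0.8416/√(77 × 2/9)) = exp(−0.2035) = 0.816. A boundary this close to 1 is sensitive to modest selection.

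**Error rate with no vaccine effect.** Simulation of 6,000 runs per cell (Monte Carlo SE about 0.005): 133 vs 67 randomized, 36% random loss in both groups, Weibull shape 1.20, median 13.8 months, 36-month uniform accrual, log rank at 77 deaths. Extra loss was then added in one group. In the score model it falls on the worst 30% by a prognostic score (log-hazard SD 0.6). In the survival model it selects on survival itself, which is near the worst case. The extra-loss sizes and both selection rules are assumptions, because the documents give no loss by arm.

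| Extra loss (points) | DC arms, score (apparent HR) | DC arms, survival (apparent HR) | Control, score | Control, survival | Unrelated to prognosis (DC / control) |
|---|---|---|---|---|---|
| 0 | 0.203 (0.991) | 0.200 (0.995) | – | – | 0.204 |
| 3 | 0.249 (0.959) | 0.279 (0.934) | 0.167 | 0.140 | 0.203 / 0.208 |
| 5 | 0.272 (0.942) | 0.353 (0.887) | 0.168 | 0.115 | 0.200 / 0.211 |
| 8 | 0.311 (0.911) | 0.478 (0.820) | 0.133 | 0.070 | 0.208 / 0.204 |

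With 175 randomized and 28% base loss, the DC-arm score model gives 0.237 / 0.263 / 0.303.

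A second model (gamma frailty variance 0.5, noisy selection of poor-prognosis patients, 4,000 runs, analysis at 48 months) shows the same pattern. Equal 40% loss gives 0.21. Loss of 42.5% DC vs 35% control gives 0.29, 45% vs 30% gives 0.33, and 35% vs 50% gives 0.11. The all-randomized test stays at 0.20–0.21 throughout.

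**Sections 9.8 and 15.3.1 side by side.** Take a patient who does not complete chemoradiation, has not progressed, and is disqualified before vaccine 1.

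- If the PI releases vaccine, the patient begins the sequence and can fall within the 15.3.1 intent-to-treat group, so there is no conflict.
- If the PI does not, 9.8 includes the patient in the intent-to-treat analysis and 15.3.1 excludes the same patient. Both rules cannot be followed.

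**The case against.** The plan's choice is explicit and reasoned. Assigned treatment does not differ before vaccine 1; the index day, control median and event count are all built from that point; and section 15.1 says the trial is not definitive and accepts a large false-positive rate. A vaccinated-set primary analysis is a legitimate choice in a phase II screening trial. This stands, and the primary test need not change. It also follows that the proposed analysis does not repair the error rates tabulated above; it lets a reader see whether they are a live issue.

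The evidence for arm-dependent loss is circumstantial. Section 9.8 lets vaccination go ahead with fewer cells than targeted, and 9.6 allows further leukapheresis, so both limit product-related loss. The log's reasons for loss do not include manufacturing failure. Many of the re-check criteria are numeric limits, and the randomization SOP cited in 9.3 is not available here and may address concealment. These points make a large imbalance less likely. They do not establish independence, and no planned output would test it.

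The conflict with 9.8 is narrow: it concerns only patients disqualified for reasons other than progression and then never vaccinated. Their number is unknown. Within that group the contradiction is real.

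**Conclusion.** The concern holds and should be fixed, in two parts of different weight.

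The conflict between 9.8 and 15.3.1 is an error as written, for patients disqualified before vaccine 1 for reasons other than progression and never vaccinated.

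The refusal of any all-randomized analysis rests on a reason that does not support it. Up to about 40% of those randomized may be excluded after randomization, with early progression among the documented causes. Bias is possible, not demonstrated, and its direction is unknown. Its size depends on assumed imbalances: 3 to 8 points of extra prognosis-related loss puts the nominal 0.20 error rate at 0.25–0.31 if it falls in the DC arms, or 0.17–0.13 if in the control arm, where it would tend to hide a benefit. Selection on survival itself widens this to 0.28–0.48 and 0.14–0.07. If loss is unrelated to prognosis the rate stays at 0.20–0.21.

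**What to change.** Leave the primary test unchanged. Before comparative survival data are seen:

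1. In 15.3.1, delete the statement refusing an intent-to-treat analysis of patients who do not reach vaccine 1.
2. Add, as a key supportive analysis reported beside the primary one, OS from the date of randomization in all randomized patients, analyzed as randomized and at the same data cut-off as the primary analysis.
3. Add a table by arm of the number, timing and reasons for not reaching vaccine 1, and seek vital status for patients who stopped earlier.
4. Make 9.8 and 15.3.1 name the same patients as belonging to the intent-to-treat analysis.

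The cost is one analysis, one table and vital-status retrieval. Section 9.1 says patients are followed until death, but follow-up of those who withdraw before vaccine 1 is not described, so some may be censored early.

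The all-randomized estimate will be diluted. With HR 0.6 acting only after vaccine 1, 60% of 200 vaccinated, and the unvaccinated hazard assumed at 1.0 to 2.5 times control, the HR is about 0.73. Power is 0.79–0.81 at the date of the 77th vaccinated-set death and 0.81–0.83 at about 51 months, against 0.90–0.91 for the vaccinated set. A separate model, with median survival of 6 to 12 months assumed for unvaccinated patients, gives an HR of about 0.75–0.76 and power of about 0.82. If the analysis were instead read at the 77th death among all randomized, power would fall to 0.54–0.62, which is why the cut-off should match the primary analysis.

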2 STUDY SYNOPSIS

Title	ATTAC-II: A Phase II Randomized, Blinded, and Placebo-controlled Trial of CMV RNA-Pulsed Dendritic Cells with Tetanus-Diphtheria Toxoid Vaccine in Patients with Newly-Diagnosed Glioblastoma
Study Drugs:	Autologous dendritic cells (DCs) derived from PBMC loaded with RNA encoding the human cytomegalovirus (CMV) matrix protein pp65 as a fusion protein with the short targeting peptide from lysosomal membrane associated protein (pp65-shLAMP) plus GM-CSF and tetanus-diphtheria (Td) vaccine as adjuvants; autologous DCs derived from PBMC loaded with pp65 RNA as a fusion protein with full-length LAMP protein (pp65-fLAMP) plus GM-CSF and Td as adjuvants; or autologous unpulsed PBMCs administered as a control vaccine.

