baseline. Grade III neurologic toxicities will be declared irreversible if they cannot be reversed within 4 weeks of clinical management. If the event has not improved to a Grade \leq II within 7 days of clinical management (then to \leq Grade I or baseline within 21 days), a DLT will be declared for that patient and no further vaccinations or study-related procedures will be performed. If the event is reversed, but Grade III NCI CTC neurologic toxicity is again seen with subsequent vaccinations, all further vaccinations and study-related procedures will be withheld and a DLT will be declared. Medical therapy or surgical intervention, may be used to reverse any toxicity if necessary.

In the case of hypersensitivity reactions, treatment measures deemed medically appropriate will be initiated and the PI notified of the event. Although not considered a DLT, any patient with \geq Grade II urticaria will not receive further vaccines and will be withdrawn from the study.

Cerebral edema toxicity exception:

Cerebral edema normally presents in glioblastoma patients as part of the disease process and can be exacerbated by standard of care chemotherapy and radiation. Furthermore, an effective anti-tumor immune response may involve inflammatory response and edema in infiltrative tumor cells.

Therefore, we propose that worsening cerebral edema (noted by MRI) that is not associated with changes in neurological symptoms will not constitute a DLT, but worsening cerebral edema in association with Grade 3 or greater other neurologic toxicities will be managed with above outlined criteria (improvement to \leq Grade 2 within 7 days and to Grade 1 or baseline within 21 days or will be declared a DLT). Radiographic improvement of cerebral edema will be noted, but since NCI CTCAE v5.0 guidelines do not allow for an improvement in cerebral edema Grade < 3 , the CTCAE grading criteria for cerebral edema will be exempted from DLT assessment.

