If a death occurs within 30 days of DC vaccine administration, that is not attributable to progressive disease or other obvious non-study related cause (i.e. motor vehicle accident), enrollment of new subjects will be suspended until review by the Protocol Chair and IND Sponsor has been completed and the FDA notified. If attribution of death is determined by the Protocol Chair, IND Sponsor or FDA to be possibly, probably or definitely related to trial drug, continued treatment of all enrolled subjects with trial drug will be suspended until the review is completed and recommendations for study continuation have been issued and approved by FDA. Any death attributed to trial drug, regardless of the timeline with respect to last treatment, will result in suspension of enrollment and suspension of continued treatment for enrolled subjects until review by FDA is complete, and recommendations for study continuation issued and approved. The IRB and DSMB will be notified of subject deaths per local policy. Deaths or life-threatening adverse events will be reported to FDA by the IND sponsors as soon as possible but no later than 7 calendar days after the sponsor's initial receipt of the information (21 CFR 312.32).

Grade	Relation to IP	Report to Coordinating Center	Report to IRB and DSMB	Report to FDA
AE Grade 3	No	Enter data in OnCore	Report per local policy	No
AE \geq Grade 2	Possible, probable or definite	Report within 24 hours via email	Report per local policy	IND sponsor will report to FDA if

				meets definition below
SAE	All	Report within 24 hours via email	Report per local policy	IND Sponsor will report to FDA within 15 calendar days if meets FDA requirement
Fatal or life threatening	All	Report within 24 hours by phone and via email	Report per local policy	IND Sponsor will report to FDA within 7 calendar days if meets FDA requirement

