13.5.3 Infection

The DC or PBMC injections may include the risk of infection due to potential contamination in the laboratory. This may result in localized redness, swelling, or induration at the injection site. In the most extreme situation, this may lead to systemic bacterial/fungal sepsis and possibly death. The probability of this risk is relatively low, given the small injection volume and the fact that the DCs and PBMCs will be strictly tested for sterility. The risk of infection due to potential contamination of the DCs and PBMCs in the laboratory will be minimized by biosafety quality assurance and testing. All cell cultures will be handled in a core tissue culture facility dedicated to the processing of human cells. Following injections, patients will be monitored throughout the course of the study for any signs and symptoms of infection. If an active infection is suspected, patients will be cultured and treated with appropriate antibiotics.

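### As worded, the safety-evaluable set counts only DC vaccine recipients, which read literally omits the PBMC control arm, and no adverse event tabulation by arm is planned

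*Combined protocol and SAP*

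**What the plan says.** Section 15.3.1 sets two evaluability rules, one after the other. For safety: "All subjects who receive at least one dose of DC vaccine will be considered evaluable for purposes of safety and toxicity". For efficacy, subjects who complete chemoradiation and receive dose-intense adjuvant temozolomide and "at least 3 DC vaccines will be considered evaluable for purposes of the primary and secondary endpoints".

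The Synopsis lists the Arm 3 product among the study drugs: "autologous unpulsed PBMCs administered as a control vaccine". Section 9.8 gives every group an intradermal immunization series. Section 13.5.3 assigns the control product a risk of its own: "The DC or PBMC injections may include the risk of infection due to potential contamination in the laboratory".

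Under Section 13.3, adverse events are collected from vaccine #1 until 30 days after the last study drug dose, with no limit by arm. Grade 2 events are recorded if they are suspected reactions, and Grade 3 or greater events are recorded in all cases. A running summary of the Grade 3 or greater events is kept and classified by organ system, grade, outcome and relation to treatment. Arm is not among the classifiers.

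Section 13.2 applies the DLT boundary to the 80 patients of the two treatment arms, against a fixed 14.3%. The automatic enrolment pause in Section 13.4 begins: "If a death occurs within 30 days of DC vaccine administration".

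**The concern.** A programmer who builds the safety set from Section 15.3.1 as written would include no Arm 3 patient. Nothing else in Section 15.3 describes a safety analysis, and no section asks for adverse event tables by arm or a contrast of DC with control.

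This matters because the events of interest have a large background. Section 13.1 says so for one of them: "Cerebral edema normally presents in glioblastoma patients as part of the disease process and can be exacerbated by standard of care chemotherapy and radiation". Every patient also receives the intramuscular Td booster with vaccine #1 (Section 9.7), and Section 13.5.10 lists headache and convulsions among the events reported after Td. Arm 3 is the one group that shows this background without DCs, GM-CSF or Td skin preparation.

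Without a table by arm, background and vaccine effect are separated only by the attribution that the PI assigns under Section 13.3, on which the DLT definition in Section 13.1 also depends. The trial is described as single-blind. That suggests, though the text does not say so outright, that the person who assigns attribution may know the arm. Section 15.1 justifies a concurrent control by the need for fair comparisons, and the safety data already collected could use it.

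**Working it through.** **1. The plan's own sizing, which needs the 40 controls.** Inputs from Section 15.2: 80 treated and 40 control patients, hazard ratio 0.60, one-sided alpha 0.20, power 90%. Schoenfeld's formula with treated fraction 2/3:

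deaths = (0.8416 + 1.2816)² / [(2/3)(1/3)(ln 0.60)²] = 4.508 / (0.2222 × 0.2609) = 77.7

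The plan states 77, at which power is 89.8%. The figure reproduces and is not in dispute.

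**2. Size of the safety set.**
- Literal wording: 80 of 120 = 67%, with 0 of 40 controls.
- At least one dose of study vaccine, DC or PBMC: 120, split 80 and 40.

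**3. Is the wording literal or loose?** Usage is mixed.
- Products kept apart: Section 9.6.3 gives different diluents for DC vaccines and PBMC vaccines, and Sections 9.8, 13.5.3 and 13.5.4 name both products.
- DC-only in other safety text: toxicity monitoring at the end of Section 9.8, the boundary in 13.2, and the 30-day death trigger in 13.4.
- Loose use for everyone: Section 9.1 has all patients repeat leukapheresis to make further DC vaccines, and Section 9.6 speaks of up to 10 DC vaccines for subjects generally.
- The efficacy sentence directly after the safety sentence cannot be literal. It would leave no Arm 3 patient evaluable for overall survival, although the same section compares Arms 1 and 2 with Arm 3.

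**4. What a by-arm comparison could show.** The documents give no control toxicity rate, so every rate below is an assumption. The 14.3% and 27.1% are borrowed from Section 13.2 as benchmarks, where they are DLT limits and not expected rates; the 5% is chosen for illustration.

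half-width = 1.96 × √[p₁(1 − p₁)/80 + p₀(1 − p₀)/40]

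For 14.3% versus 5%: 1.96 × √(0.001532 + 0.001188) = 1.96 × 0.0521 = 0.102.

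| DC | Control | Difference (points) | 95% half-width (points) | Power, two-sided 0.05 |
|---|---|---|---|---|
| 14.3% | 14.3% | 0 | 13.3 | – |
| 14.3% | 5% | 9.3 | 10.2 | about 30% |
| 27.1% | 14.3% | 12.8 | 14.6 | about 34% |
| 27.1% | 5% | 22.1 | 11.9 | about 88% |

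Power is Φ[(difference − 1.96 × pooled standard error) / unpooled standard error]. Of the three non-zero differences, only the largest has an interval that excludes zero.

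**5. The DLT boundary.** An exact recursion over the 80 printed limits gives a stopping probability of 0.047 at 14.3% (stated 0.05) and 0.7995 at 27.1%, consistent with the stated more than 80% above that rate. The rule tests a fixed rate and does not use Arm 3, so this point does not affect it.

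**The case against.** The strongest reply is that this is a slip. The plan uses the term loosely for all arms elsewhere, and the adjacent efficacy sentence must be a slip. The safety sentence says who is evaluable; it does not say that controls are excluded or unreported. This largely stands, and it is why the point concerns wording and a missing table and does not allege a deliberate exclusion. It does not remove the point. The other safety passages are also DC-only, the amendment log records the 20190415 revision of Section 15.3 as a clarification of evaluability, and this sentence is the only safety-set definition. An analyst should not have to guess about one third of the vaccinated patients.

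A reader might infer that toxicity will be reported with no concurrent comparator at all. The documents do not support that. Arm 3 events are collected from vaccine #1, serious events are reported whatever their cause, and the Grade 3 or greater summary covers all patients. What is missing is the split by arm.

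A reader might also infer that the decision to go to phase III would rest on an uncontrolled safety table. It would not: Sections 5.2.1 and 15.2 rest that decision on overall survival against Arm 3, and safety is not a listed objective.

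On Section 13.4, a death attributed to trial drug already suspends enrolment and treatment whatever its timing, so the DC-only trigger is not shown to be an error.

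**Conclusion.** The point holds in a limited form and should be corrected. Read literally, Section 15.3.1 leaves 0 of about 40 controls in the safety set (80 of 120 vaccinated patients remain), in conflict with adverse event collection in all arms. Under either reading, literal or loose, no between-arm safety tabulation is specified.

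No stated figure in the plan changes. The gain from the correction is descriptive: with 80 and 40 patients, and rates that are assumptions throughout, a difference would be known to within about 10 to 15 points, and only a large one would be clear. The contrast would also describe the whole DC package (DCs, GM-CSF and Td skin preparation) against PBMCs with saline, not the DCs alone.

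The parallel efficacy sentence has the heavier literal consequence, because it would remove Arm 3 from the primary endpoint set. The context shows that this cannot be intended.

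**What to change.** - In Section 15.3.1, define the safety set as all subjects given at least one dose of study vaccine, DC or PBMC, analysed by the product received.
- Add that adverse events are tabulated by arm and for Arms 1+2 versus Arm 3, regardless of attribution, with differences and 95% intervals shown as descriptive. For Grade 2 events, note that only suspected reactions are recorded, so the attribution-free table covers Grade 3 or greater.
- In the next sentence, replace the three-DC-vaccine requirement with three doses of study vaccine, DC or PBMC, so that Arm 3 stays in the endpoint set. Check the evaluable-subject wording in Section 9.8 for the same slip.
- Leave the Section 13.2 boundary on DC recipients.
- Ask the sponsor to reconcile the DC-only 30-day death trigger in Section 13.4 with PBMCs being a listed study drug. No rule is proposed here.

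The cost is a few words and an extra column in the safety tables. The data are already collected, so no new visits or procedures are needed.
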